### 14.2.3 Survival to Hospital Discharge

While this study is not designed to evaluate associations with survival to hospital discharge, we will nonetheless monitor and assess this outcome.

### 14.2.4 Neurologically-Intact Survival to Hospital Discharge

While this study is not intended to have adequate power to detect associations with neurologically-intact survival to hospital discharge, we will nonetheless monitor and assess this outcome. MRS has concurrent validity with other measures of neurological recovery after stroke and brain injury. MRS has been previously used in a cohort of neurosurgical patients with in-hospital cardiac arrest, a cohort of survivors of OHCA, and a cohort of survivors of arrest in either setting.

Neurologic status at discharge will be assessed using the modified Rankin Score (MRS), which can be determined through medical record review. The MRS uses a seven-point ordinal scale; 0 (no symptoms at all) to 6 (death). Patients who die before discharge will be assigned an MRS of 6. For analytic purposes, MRS at discharge is often dichotomized to MRS ≤3 (“good”) vs. 4-6 (“poor”).

## 14.3 Adverse Events

The trial will identify a range of out-of-hospital and in-hospital adverse events information to help assess the safety of the interventions.

### 14.3.1 Unexpected Adverse Events (UAE)

These will be defined as any serious unexpected adverse effect on health or safety or any unexpected life-threatening problem caused by, or associated with the interventions if that effect or problem was not previously identified in nature, severity, or degree of incidence in the investigation plan or application (including a supplementary plan or application), or any other unexpected serious problem that relates to the rights, safety or welfare of subjects. The death or neurological impairment of an individual patient is not considered an unexpected adverse event in this study.

### 14.3.2 Expected Adverse Events

The following are events commonly observed in patients who experience cardiac arrest or resuscitative efforts after its onset, or who receive airway management efforts, and may or may not be attributable to specific resuscitation therapies. These events will be monitored and reported but not considered as adverse events of the study intervention.

- **Unsuccessful EMS airway insertion.** This event includes unsuccessful EMS ETI or LT insertion efforts. This event does not include ED airway insertion efforts. This event will be determined from EMS records.
- **Multiple EMS airway insertion attempts.** This event includes 3 or more EMS attempts to perform ETI, or 3 or more EMS attempts to insert the LT. This event does not include ED airway management efforts. This event will be determined from EMS records.
- **Unrecognized EMS airway misplacement or dislodgement.** This event includes unrecognized EMS endotracheal tube placement in the esophagus or hypopharynx, or displacement of a correctly placed ET tube. Airway misplacement and dislodgements are difficult to differentiate; this trial will not differentiate these events. Airway misplacement/dislodgement events will be determined from EMS and ED records.

This event does not include right mainstem intubations. This event does not include instances where EMS personnel immediately recognize and correct ET tube misplacement. This event does not include ED airway misplacements.

Misplacement and dislodgement events are unique to ETI and do not apply to the LT.

- **Inadequate EMS ventilation.** This event includes instances where EMS personnel a) perceive that a successfully inserted airway device is resulting in inadequate ventilation and b) therefore opt to change to another airway management device or technique. Inadequate ventilation connotes a) inability to insufflate any oxygen (airway obstruction) or b) inadequate chest rise on insufflation. Potential reasons for inadequate ventilation may include device obstruction, misplacement, malfunction or cuff leak, among others.

Inadequate ventilation will be based upon EMS personnel assessment, and will be determined from EMS patient care records.

- **Airway swelling or edema.** A described complication of the LT is the development of major tongue, pharyngeal or hypopharyngeal swelling, which may interfere with ventilation. While usually associated with instances of prolonged LT ventilation (several hours), some clinicians have reported the occurrence of this event during resuscitative efforts. This event

will be based upon EMS and ED personnel assessment and will be determined from EMS and ED patient care records. The timeframe for surveillance for this event will be limited to the earlier of a) replacement of the LT with an ET tube, or b) the first 24 hours of hospitalization. While generally associated with LT insertion, we will monitor the occurrence of airway swelling or edema regardless of inserted airway device.

- **Oropharyngeal or hypopharyngeal injury.** Advanced airway insertion may result in injury to the oropharynx and hypopharynx, including soft tissue lacerations, injury to teeth, and perforation of pharyngeal, hypopharyngeal or other anatomic structures, among others. This event will be determined by review of the discharge summary and ED physician records and will be limited to injuries identified during the first 24 hours of hospitalization.
- **Pneumothorax.** Airway insertion and ventilatory efforts may cause pulmonary barotrauma, resulting in pneumothorax. This event will be determined from radiology or ED physician interpretation of the first chest x-ray or computed tomography (CT) performed in the ED.
- **Pneumonia and aspiration pneumonitis.** Pneumonia and aspiration pneumonitis are known sequelae of cardiac arrest and airway management. This event will be defined as the presence of an infiltrate or consolidation as reported by radiology interpretation of chest x-rays or computed tomography (CT) performed during the first 72 hours of hospitalization.

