## **12.5 Protocol Considerations**

### **12.5.1 Number of Airway Insertion Attempts**

Successful ETI or LT insertion may require multiple attempts. With “attempt” defined as passage of the laryngoscope blade into the mouth, Wang, et al. observed that first-attempt success for paramedic ETI of OHCA was 70%, with up to four attempts needed to reach the 90% success threshold. EMS practitioners generally try to minimize the number of ETI attempts because of the propensity of oral injury and because multiple attempts may signal ETI futility and the need to proceed to alternate airway management techniques. In clinical practice, some EMS protocols limit practitioners to 3, 2 or even 1 unsuccessful ETI attempt before proceeding to alternate “rescue” airway measures.

This trial will not dictate or limit the number of ET tube or LT insertion attempts. However, we will monitor the number of insertion attempts for each device. Training for the trial will emphasize a)

definition of “ETI attempt” as insertion of laryngoscope between the teeth (not insertion of ET tube), b) definition of “LT attempt” as insertion of LT airway between the teeth, c) methods for reporting the number of attempts for each airway device, and d) strategies for minimizing ETI or LT insertion attempts.

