### **12.5.2 Unsuccessful Airway Insertion and Rescue Interventions**

An important metric in this study is the rate of unsuccessful ETI or LT insertion and the need for rescue airway interventions. While success rates for OHCA ETI and SGA insertion in OHCA are relatively high (approximately 90%), the time-critical nature of OHCA requires that rescue airway interventions be initiated promptly. Clinical signs of airway insertion or ventilation failure include the inability to place the airway, inability to confirm proper airway device placement, detectable air leak on insufflation resulting in suboptimal chest rise.

In the event that EMS personnel are not able to insert or ventilate through the assigned airway, they may revert to any alternate airway management strategy. For example, if the patient is assigned to ETI but intubation efforts are unsuccessful, EMS personnel may revert to bag-valve-mask ventilation or LT insertion. Conversely, if the patient is assigned to LT but insertion efforts are unsuccessful, EMS personnel may revert to bag-valve-mask ventilation or ETI. In all cases, subjects will be analyzed by their assigned treatment, per intention-to-treat principles.

While select EMS agencies may carry additional SGA other than the LT, during training we will encourage the use of LT as the preferred rescue device in the event of unsuccessful ETI.

Alternate intubation techniques (nasotracheal intubation, digital intubation, etc.) may be used in a rescue capacity in the event of failed initial orotracheal intubation or LT insertion.

Some EMS agencies perform needle jet ventilation or open cricothyroidotomy. This trial does not preclude the use of these techniques in the event of unsuccessful initial airway insertion.

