**Table 2 – Potential EMS Airway Intervention Combinations**

number of ETI attempts (successful or unsuccessful) and number of LT attempts (successful or unsuccessful).

- **Successful airway insertion time.** EMS personnel will report the time of successful ETI or LT insertion.
- **Airway course in receiving Emergency Department.** The purpose of these data is to ascertain how the receiving ED utilizes airway devices placed by EMS personnel. Research coordinators will review ED records to determine the course of airway management during initial ED resuscitation. For cases arriving at the ED with ongoing CPR, this time period encompasses the time elapsed until the achievement of ED ROSC. For cases arriving at the ED with ROSC, this time period encompasses the first 20 minutes in the ED.

These data do not pertain to airway interventions performed after the achievement of ROSC (for those arriving with ongoing CPR) or after the first 20 minutes in the ED (for those arriving at the ED with ROSC). Potential EMS/ED airway interventions are summarized in Table 3.

EMS Airway Intervention on ED Arrival	ED Airway Intervention
ETI LT BVM Other Airway	Continue use of EMS airway Replace with ED ETI Replace with other ED airway

Table 3 – Potential Emergency Department Airway Interventions

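### The multiple-attempts event in Section 14.3.2 counts each device separately, so attempts split between ETI and LT are missed; add a total ETI + LT event

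*Combined protocol and SAP*

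**What the plan says.** Section 14.3.2 lists multiple EMS airway insertion attempts among the expected adverse events: "This event includes 3 or more EMS attempts to perform ETI, or 3 or more EMS attempts to insert the LT". The event comes from EMS records and leaves out ED airway efforts. Nothing in the definition adds attempts across devices.

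Four other places bear on it.

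- **Section 12.5.1, no trial limit.** "This trial will not dictate or limit the number of ET tube or LT insertion attempts". The same section says that in practice "some EMS protocols limit practitioners to 3, 2 or even 1 unsuccessful ETI attempt before proceeding to alternate" airway measures.
- **Section 12.5.2, crossing devices.** After failed intubation, "EMS personnel may revert to bag-valve-mask ventilation or LT insertion"; the converse is allowed in the LT arm. The section adds that "during training we will encourage the use of LT as the preferred rescue device in the event of unsuccessful ETI".
- **Section 14.2.2, data collected.** For each subject, crews report separately the "number of ETI attempts (successful or unsuccessful) and number of LT attempts".
- **Section 3 (Outcomes) and Section 15.4, analysis.** The number of insertion attempts belongs to the secondary outcome on airway course. Airway course and adverse events are both compared between the interventions.

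**The concern.** The trial compares two strategies: ETI first with rescue as needed, and LT first with rescue as needed. For a strategy, the patient's burden is the number of times a device was put into the airway, whichever device it was. Section 12.5.1 names oral injury as one reason for keeping ETI attempts few, and the Summary lists repeated intubation attempts among the pitfalls of ETI.

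A threshold applied to each device separately misses patients whose attempts are divided between devices. Training steers failed intubations toward LT, so this is an expected route. The local limits that the protocol describes are limits on ETI. Where they are one or two, they move later attempts to the LT count, which starts again from zero. The loss would then fall mainly on the ETI arm, and a real excess of repeated attempts there could look smaller than it is. Crossover gives both arms the same agencies but does not cure this, because an ETI limit acts chiefly in the periods when ETI comes first.

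**Working it through.** The documents state no expected rate for this event, so there is no figure to reproduce. The check has two parts.

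**1. Which patterns count.** Per-device rule: event if ETI ≥ 3 or LT ≥ 3. Total rule: event if ETI + LT ≥ 3.

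| ETI attempts | LT attempts | Total | Per-device event | Total-count event |
|---|---|---|---|---|
| 1 | 1 | 2 | no | no |
| 1 | 2 | 3 | no | yes |
| 2 | 1 | 3 | no | yes |
| 2 | 2 | 4 | no | yes |
| 3 | 0 | 3 | yes | yes |
| 2 | 3 | 5 | yes | yes |

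A patient with four attempts split evenly is not an event; a patient with three ETI attempts is. If ETI stops at one or two attempts for the patient, the ETI half of the definition is not reached. A limit of three masks nothing.

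**2. Illustration of size.** Input from Section 12.5.1: "first-attempt success for paramedic ETI of OHCA was 70%, with up to four attempts needed to reach the 90% success threshold". So 30% are unplaced after one attempt and 10% after four.

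Assumptions: equal conditional failure on attempts 2 to 4; every failure continues up to the local limit; every failure at the limit goes to LT; LT success per attempt p = 0.8 to 0.9. The value of p is assumed, since the documents give no per-attempt figure.

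- Conditional failure per later attempt: (0.10 / 0.30)^(1/3) = 0.693.
- Unplaced after two ETI attempts: 0.30 × 0.693 = 20.8%. Without the interpolation, the figure must lie between 10% and 30%.
- **No ETI limit, or a limit of three:** these patients have a third ETI attempt and are counted, 20.8%. With 1,306 per group (Section 16.1), that is 0.208 × 1,306 = 272 patients (bounds 131 to 392).
- **Limit of two, then LT:** the same 20.8% have at least three attempts in total. The per-device rule counts only those needing three LT attempts: 20.8% × (1 − p)² = 0.83% at p = 0.8 and 0.21% at p = 0.9.
- **Limit of two, half reverting to bag-valve-mask instead:** 10.4% have three or more in total, and 0.1% to 0.4% are counted.
- **Half of patients in agencies with a limit of two or fewer:** the rate counted through ETI falls from 20.8% to 10.4%, or 136 of 1,306 (bounds 65 to 196).

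Sensitivity: Section 5.1 says one-fourth of ETI efforts needed two or more attempts, citing the same reference. Starting from 25% with the same factor gives 0.25 × 0.693 = 17.3% instead of 20.8%.

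**The case against.** Much of the case on the other side stands.

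- **The patients are not lost.** Failed intubation followed by LT rescue falls under the separate event of unsuccessful EMS airway insertion in Section 14.3.2. That event carries no count, however: one failed ETI attempt followed by one LT attempt scores the same as 2 ETI + 2 LT.
- **Attempt burden is already compared.** Per-device counts are part of a secondary outcome analyzed by arm. Only a prespecified sum is missing.
- **The event is minor.** It is one of eight expected events, is not named in the adverse-event list in the Summary, and is not treated as an adverse event of the intervention. Neither the primary analysis nor a stopping boundary uses it.
- **A per-device threshold is a coherent measure of device difficulty.** That is a reason to keep it.
- **A total count also varies with local practice.** With a limit of one and LT rescue for all failures, three or more total attempts occur in 30% × (1 − p) = 3% to 6%, against 20.8% with a limit of two or none. That variation, though, reflects attempts the patient actually had.

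A reader might infer that the safety comparison simply measures agencies' attempt limits instead of the strategies. The documents do not support this. No between-agency comparison of the event is planned, randomization is stratified by site, every cluster crosses over (Section 13.1), and Section 12.5.1 speaks only of some EMS protocols. It is also too strong to say that the ETI half can never occur under a limit of one or two. The text limits practitioners, so whether the limit is per person or per patient is unclear, and alternate ETI techniques are allowed as rescue.

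**Conclusion.** The point holds as a limited gap in an event definition. The per-device threshold leaves out patients with three or more attempts divided between ETI and LT. Where ETI is limited to one or two attempts, it can understate repeated attempts in the ETI arm.

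The size in this trial is unknown, because the participating agencies' limits are not given. The illustration (about 21% unplaced after two ETI attempts, with under 1% counted under a limit of two and LT rescue) rests on the interpolation, universal LT rescue and an assumed LT success of 80% to 90% per attempt. It shows how far the definition can move the count and does not forecast the trial's result.

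A reader might also conclude that the per-device event should be replaced, or that the sum should cover every airway device. Neither follows. The per-device event answers a valid question, and Section 14.2.2 provides attempt counts for ETI and LT only.

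**What to change.** Keep the existing event and add one to Section 14.3.2, for example: *Total EMS insertion attempts: 3 or more ETI and LT attempts combined in the same patient, summed from the counts reported under Section 14.2.2 and compared by assigned arm.* Attempts keep their Section 12.5.1 definitions. Attempts with other devices stay outside the sum, because including them would need new definitions and fields.

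The cost is one sentence and one derived variable, with no new data collection. The downside is one more event to report, with a higher rate than the per-device event and less comparability with single-device series. The change concerns measurement only and proposes no clinical limit on attempts.

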## 12. Interventions

### 12.1 EMS Personnel Training Levels

The interventions in this trial may involve coordination between advanced- and basic-level EMS personnel.

- Advanced-level EMS personnel (Advanced Life Support, ALS, paramedic, advanced care paramedic) perform advanced-level interventions, including intravenous drug administration, manual defibrillation, and advanced airway management interventions (ETI and SGA).
- Basic-level EMS personnel (Basic Life Support, BLS, Emergency Medical Technician, EMT) perform basic measures such as CPR and automated defibrillation. Bag-valve-mask ventilation is their primary airway management intervention, although select EMS agencies may perform SGA (LT) insertion. In general, basic-level EMS personnel in the US do not perform ETI.

[figure not shown]
EMS organization and response to OHCA vary across ROC. In some EMS agencies, all responding personnel are trained at the advanced level. In other agencies, OHCA care is tiered, with both basic-level and advanced-level EMS personnel responding to OHCA. Select BLS EMS personnel among ROC EMS agencies perform SGA insertion (Table 2). The trial design will try to accommodate all configurations of EMS response.

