#### **12.5.6 Emergency Department Management of the EMS Airway Device**

Most trial patients will be transported to a receiving ED for continued resuscitation care. There are currently no clinical practice guidelines for the ED management of an EMS-placed ET tube or SGA. In general, ED practitioners will verify placement of the EMS ET tube, although practices vary widely. If the ET tube is determined to be misplaced or insufficiently ventilating, ED physicians may opt to remove and replace the tube.

With SGA such as the LT, ED practices similarly vary, with some practitioners leaving the airway in place for the duration of resuscitation and others opting for immediate replacement with ETI. There are no national practice guidelines for the ED management of an EMS-placed SGA, although select textbook chapters offer practical guidance.

In practical terms, if the EMS-placed LT is functioning well, ED practitioners may continue using the device, deferring ETI until there is restoration of pulses. In contrast, if there is evidence that the LT is malfunctioning, immediate replacement with ETI or another SGA may be indicated. Replacement of the LT with ETI may occur with a variety of approaches including exchange over a gum elastic bougie (Eschman tube), bronchoscopic replacement over an Aintree catheter, or removal and ETI using direct laryngoscopy.

The pragmatic scope of this trial will focus on out-of-hospital EMS management of the airway. This trial will not dictate practices for ED management of EMS-placed airways. However, in preparation for the trial we will provide receiving ED with guidelines on best practices for the management of EMS-placed airways. The guidelines will outline strategies for:

- ED verification of EMS-placed ET tubes, including the use of at least two confirmatory techniques as well as the use of end-tidal carbon dioxide detection.
- Decision points for immediate replacement of an EMS ET tube.
- Management of EMS-placed LT airways, including methods and decision points for continued use or replacement with an ET tube.

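### Device failure first found in the ED can count as a safety event for the ET tube, but has no equivalent event for the LT

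*Combined protocol and SAP*

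**What the plan says.** Section 14.3.2 (Expected Adverse Events) defines *inadequate EMS ventilation* by two joined conditions. EMS personnel must "perceive that a successfully inserted airway device is resulting in inadequate ventilation and b) therefore opt to change to another airway management device or technique". The assessor and the source are then fixed: "Inadequate ventilation will be based upon EMS personnel assessment, and will be determined from EMS patient care records". No ED assessment or ED record is named.

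Two neighbouring events in the same section are handled differently:

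- Unrecognized misplacement or dislodgement: "Airway misplacement/dislodgement events will be determined from EMS and ED records". It is limited to one device: "Misplacement and dislodgement events are unique to ETI and do not apply to the LT".
- Airway swelling or edema, for any inserted device: it "will be based upon EMS and ED personnel assessment and will be determined from EMS and ED patient care records".

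Section 14.2.2 has coordinators review ED records for the early airway course. Its Table 3 lists three ED actions (keep the EMS airway, replace it with ETI, replace it with something else) and no reason for replacement.

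Two other places are worded more broadly than 14.3.2. The Summary (Section 3) names poor ventilation leading to an airway exchange among the adverse events that form a secondary outcome, without limiting who observed it or in which record. Section 22.2 gives the hospital discharge summary as the source for expected adverse events in general.

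**The concern.** The protocol itself foresees an LT arriving at the hospital in poor working order. Section 12.5.6 says that "if there is evidence that the LT is malfunctioning, immediate replacement with ETI or another SGA may be indicated". That is the situation in which a failed LT would come to light, and it lies outside the only source named for the ventilation event. For the ET tube, the most prominent form of failure found on arrival, misplacement, has its own event, and that event does use ED records.

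At stake is a named secondary safety comparison. Section 15.4 analyses adverse events by arm, Section 16.2 lists safety by treatment group among the factors in a stopping decision, and Section 22.2 has the DSMB compare adverse event rates between arms. Appendix 4 adds that, if survival does not differ, practitioners may choose the device that suits their setting. In that case the safety tables would carry much of the practical message. A list that can register ED-detected failure for one device more readily than for the other is a weak basis for it.

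**Working it through.** No arithmetic applies. The plan states no rate for this event and no rate of device failure detected in the ED. The check is to apply the definitions in 14.3.2 to each way in which an inserted device can fail.

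| Situation | Inadequate-ventilation event? | Other listed event? |
|---|---|---|
| Crew notices poor ventilation and changes device or technique (either device) | Yes | Possibly |
| Crew notices but keeps the device (either device) | No, second condition fails | Only if another event applies |
| Crew does not notice; ED finds the ET tube misplaced or dislodged | No, both conditions fail | Yes, misplacement/dislodgement, from ED records |
| Crew does not notice; ED finds the LT malpositioned | No, both conditions fail | No, misplacement is declared not to apply to the LT |
| Crew does not notice; ED finds the LT obstructed or leaking | No | No |
| Crew does not notice; ED finds a correctly placed ET tube obstructed or leaking | No | No |
| Swelling that impairs ventilation, either device | Only if the crew noticed and changed | Yes, swelling, from EMS and ED records |

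Three things follow.

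1. The third and fourth rows carry the asymmetry. The same kind of fault, a device in the wrong position and first recognised in the ED, is an event for the ET tube and not for the LT. Yet the ventilation definition itself lists misplacement among the possible causes of poor ventilation, without restricting it to one device.
2. The asymmetry is not total. Obstruction or leak of a correctly placed ET tube first found in the ED is missed as well, and swelling is captured for both devices.
3. The asymmetry attaches to the device in place. It therefore carries over to the arms to the extent that the device in place follows assignment; a rescue LT in the ETI arm is subject to the same gap.

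**Can the data from 14.2.2 fill the gap?** They record that a replacement took place, within a window: until ROSC in the ED for patients arriving in arrest, or the first 20 minutes for those arriving with a pulse. Section 21 encourages EDs to go on using a working LT and to convert after ROSC. For patients arriving with a pulse, planned conversion can therefore fall inside the window beside replacement of a failed device. For patients arriving in arrest, Section 12.5.6 notes that some practitioners replace the LT at once. Without a reason, the two kinds of replacement cannot be told apart in either group.

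**The case against.** **The definition may be intended.** The trial is pragmatic and concerned with EMS care. The Summary's own wording makes an exchange part of the outcome. Section 14.3.2 says that the listed events are monitored but not treated as adverse events of the intervention. ED replacement is already abstracted, and Section 22.2 has staff report all potential adverse events in structured and open form. The abstraction form and Manual of Operations are not in the documents, so a reason may be collected there. Much of this stands. It supports keeping the present event intact as one limb, and it means one can say only that the protocol lists no reason. It does not explain why ED records are accepted for ET tube misplacement and for swelling but not for ventilation failure, and an open-form report is not a tabulated endpoint.

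**A reader might infer a stronger point:** that crew capability biases the event in favour of the LT, because "In general, basic-level EMS personnel in the US do not perform ETI" and such a crew would have less to switch to. The documents do not support this. A change of technique is enough, so moving from the LT to the mask qualifies. Under Section 12.3 advanced personnel place the LT as primary airway, and basic-level insertion is optional. Section 12.5.2 lets crews in either arm revert to the mask or to the other device. Its encouragement of the LT as rescue concerns failed ETI, not a tube already placed. The direction of any difference in crew switching is therefore unknown, and significance tests on assumed switching rates would show only what was assumed.

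**A reader might also infer** that a failure found in the ED is never an event of any kind. That is too broad, given misplacement, swelling and the recorded replacement itself.

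**Conclusion.** The point holds as one of uneven ascertainment. A misplaced ET tube recognised in the ED is a listed event; an obstructed, leaking or malpositioned LT recognised there is not an inadequate-ventilation event, and only swelling partly covers it. This rests on reading the sentence on assessor and source in 14.3.2 as restrictive, although the definition is introduced as what the event includes. It also rests on the absence of a reason for replacement in 14.2.2.

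The size of the under-count cannot be derived, and no biased between-arm difference has been demonstrated. Nothing here touches 72-hour survival. It is a modest defect in a named secondary safety outcome and worth correcting because the correction is cheap.

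**What to change.** In 14.3.2, report inadequate ventilation in three limbs:

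- (i) the event as now defined, unchanged;
- (ii) poor ventilation through an inserted device that the crew documents without changing device or technique;
- (iii) non-ventilation of the EMS device on arrival, as documented by the ED.

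For limb (iii), add one item to the ED abstraction already planned in 14.2.2, the reason for replacement: *not ventilating*, *elective* or *not documented*. Show each limb separately by assigned arm, with transported patients as the denominator for limb (iii). State how many limb (iii) cases are also counted as ET tube misplacement, so that the overlap is visible. Reconcile the Summary, 14.3.2 and 22.2 on definition and source.

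The cost is one definition edit and one form item; clinical care does not change. If abstraction has begun, earlier charts must be revisited or limb (iii) reported from the date of the change.

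The plan should state two downsides. Limb (iii) conditions on transport, which occurs after randomization, so it is not a clean comparison of arms. The ED reasons are also unblinded and arise under different replacement practice: Section 12.5.6 notes immediate LT replacement by some practitioners, while Section 21 favours keeping the EMS ET tube. For both reasons limb (iii) should stand beside limb (i) and not be pooled with it.
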